Title: EFFECT OF MONOCHROMATIC LIGHT ON THE INCIDENCE OF EMERGENCE DELIRIUM IN CHILDREN; A SINGLE BLINDED RANDOMIZED CONTROLLED TRIAL

Protocol ID#: H-39878

Drafted 9/8/17

IRB submit 8/15/17

Collaborators:

[name], MS- Principle Investigator

[name], MBA, FAAP

Background:

Emergence delirium/emergence agitation (ED/EA) is a behavioral phenomenon of unclear etiology consisting of short lived behavioral changes that can be both traumatic to families and pose a safety risk to patients and staff. ED is characterized by a variety of presentations, including crying, excitation and agitation, that occur during the early stage of recovery from general anesthesia, generally in the first 30 minutes.

Involuntary activity in the bed and even thrashing about during an episode of ED can lead to dislodgement of IV cannulas, surgical dressings and or surgically placed items such as drains and catheters.

Emergence delirium occurs in children of all ages following an anesthetic with halogenated agents (e.g. sevoflurane/isoflurane) with or without having undergone a surgical procedure (e.g. MRI patients). Electroencephalograms (EEG) in patients experiencing emergence delirium show diffuse background slowing. Presently, the treatment for ED is to revert the patient back to a hypnotic state mainly with sedatives so that they may “reset” themselves postulating that by re-inducing a hypnotic state, the brain has time to resolve this issue. The hypothesis of this study is that during ED, there is failure of organized EEG activity, especially alpha wave activity and that by enhancing alpha activity, the incidence of ED may be reduced without the need for additional pharmaceuticals which may be costly, delay recovery and are not without adverse effects specifically cardiopulmonary depression.

Monochromatic light (ML) has been used in a variety of clinical and non-clinical applications to affect a variety of changes. Exposure to light of short wavelength within the visible spectrum (450-470nm) has been associated with effects on circadian rhythm, neuroendocrine and neurobehavioral changes and enhanced cognitive performance. Blue ML has been studied safely to enhance work-place alertness and productivity. Clinically, blue ML has been used safely for decades in the neonatal intensive care unit to treat jaundice.

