Blue ML, has been known to suppress melatonin secretion and enhance alertness and workplace performance. The effect occurs within the retinal photoreceptive ganglion cells which mediate

the observed responses. The effect is even present in visually blind persons lacking outer retinal function. Short exposure to bursts of blue light has revealed enhanced neural activity on functional MRI. Use of blue ML has been shown to enhance EEG activity in the alpha range (awake range) compared with light of greater wavelengths. If using blue ML in the operating room may enhance alpha EEG activity, (a circadian marker for alertness) it may be possible to reduce the incidence of emergence delirium in the post-operative period and therefore the amount of (non-pain) sedative medication needed in recovery.

Purpose:

Emergence delirium is associated with a safety risk to patients and staff members in the fact that these children are uncontrollable and often thrashing which may result in self-inflicted injury (falls and collision with bedframe) or perturbation of intravenous or surgically placed devices. At present, the treatment involves re-sedating these patients (e.g. propofol or dexmedetomidine). These medications are certainly not without risk. If intravenous access has been lost, intra-nasal or intra-muscular administration of medications can be dangerous or impractical to administer at times of delirium.

The primary aim of this study is to ascertain if perioperative exposure to non-invasive monochromatic blue light can reduce the incidence of emergence delirium.

The secondary aim involves assessing the need for rescue interventions (e.g. hypnotic agents – propofol or dexmedetomidine).

Protocol/Risk/Subjects:

Patient identification

Patients ages 2-6 years undergoing routine tonsillectomy and adenoidectomy requiring general anesthesia would be identified for inclusion. Exclusion criteria would include: American Society of Anesthesiology classification other than 1,2; history of migraine headaches, ocular disorders, seizure history, psychiatric conditions, parental refusal, developmental delay and those patients on medication for attention deficit disorders or caffeine stimulants. Patients with contraindications to receiving inhalation agents, use of premedication with midazolam or dexmedetomidine would also be excluded.

Randomization

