A standard and routine anesthetic will ensue for these patients in line with routine operative practices at Texas Children's Hospital, including an inhalational induction (mask) using sevoflurane 8%v/v with oxygen/nitrous oxide 3/7 L/min respectively, followed by intravenous cannula placement. Propofol will be administered if needed to facilitate oral endotracheal intubation at the discretion of the anesthesia attending. Dexamethasone (0.5mg/kg), ondansetron (0.1mg/kg) and morphine (0.1-0.2mg/kg) will be administered for anti-inflammatory, antiemetic and analgesic effects respectively. Intravenous fluid (lactated ringer solution) will be continuously infused with the appropriate volume to be determined by the anesthesia provider. Maintenance of anesthesia will be with sevoflurane with the concentration titrated to maintain an appropriate level of hypnosis as determined by the anesthesia provider. At the conclusion of the surgery, the patient will undergo routine deep extubation according to the routine practice of the anesthesia providers of record. On arrival to the PACU, the Drager phototherapy lamp will be illuminated over the patient's head and neck. Randomization will determine if the patient will be exposed to ML blue light or the placebo bulb (white bulb with blue over coating). The PACU staff and the anesthesiologist will be blinded to study arm. The placebo bulb will provide blue light of all wavelengths as to not compromise blinding. The light will remain active and over the patient until the patient has been in the post anesthesia recovery unit (PACU) for 30 minutes.

Postoperative evaluation for emergence delirium

Two PACU nurses blinded to the patient group will be asked to complete the PAED scoring scale for evaluation of emergence delirium. They will be asked to complete the scoring evaluation upon arrival to the PACU and at 10 minutes, 20 minutes and 30 minutes following arrival. Two nursing evaluations will be used to reduce inter-observer bias. A patient

experiencing emergence delirium will receive standard pharmacologic treatment as determined by the anesthesiology provider irrespective of study participation. Blinding of the nurse and anesthesia team will help to ensure that the nursing staff will call the anesthesia providers with any and all usual questions and the anesthesia provider to react and treat potential ED as per usual practice without being biased by the study.

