The study will end at this point without the need for additional follow-up or patient contact related to the study.

Statistical Analysis Plan

Sample size/Data Analysis:

The PAED behavioral scale will be used to assess the incidence of emergence delirium. The PAED scale is a reliable tool to measure ED and involves five items: eye contact, purposeful actions, awareness of the surroundings, restlessness, and inconsolability. While other scales exist, the PAED scale is the standard for assessment of ED and is the only validated scale. A PAED score of >12 will be used to define ED.

Cohort means and standard deviations (SD) or counts and frequencies as appropriate for the variables collected. We will compare the blue light and Sham groups using the Student's t-test for continuous variables (e.g., age, PAED score) and the chi-square test for categorical variables (e.g. % female, ASA category). For counts < 5, the Fisher's exact test will be used. For baseline comparisons, absolute standardized differences instead of p-values will be used to compare the groups.

Given the prospective collection of data, missing data for the PAED scores over time indicated a patient woke up or experienced emergence delirium and so no imputation will be performed. To adjust for any remaining confounding among the variables collected, a logistic regression model with the outcome being emergence delirium and a second logistic regression model with the outcome being either ED or the patient had a PAED score of 12 or more at time periods 10, 20, and 30 min. Both regression models used as independent predictors the following variables: treatment group, age, weight, gender, and ASA category. Robust standard errors were derived to account for any within-cluster correlation at the individual nurse level given the possible serial correlation of outcomes within each nurse caring for his or her patients.

An a priori calculation of sample size was done using an incidence of 40% of emergence delirium in similar patient population. We assumed an absolute reduction of 25% (ie, 40% to 15%) in incidence of emergence delirium to be clinically significant. To detect this difference at 80% power with a two-sided alpha of 0.05, required a sample size of 98 participants.

All p-values < 0.05 were considered statistically significant.

Risk/Discomfort:

The study procedure poses no additional risk to patients. The major risk is loss of confidentiality.

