Use of monochromatic light has been safely tested in numerous human studies and used routinely in the NICU without identified patient risk using the same Drager machines at TCH. The moment the patient is awake and making purposeful eye contact with the PACU RN, the lights will be terminated. The risk of phototherapy is well known from nearly 40 years of clinical use in neonates. The risk of phototherapy is predominantly in neonates, especially preterm infants with jaundice, all requiring prolonged and continuous exposure to high intensity light for many days. This study will not include any neonates (with immature retina) or long term exposure of >30 min. The study will be terminated the moment the patient is awake and making purposeful eye contact with the PACU RN to avoid unnecessary discomfort.

Benefits:

The study benefits include improved understanding of emergence delirium and potential for both reduction in the incidence of emergence delirium and the use of pharmacologic agents.

Consent procedures:

The parental or legal guardian permission form will be signed prior to the beginning of surgery.

Confidentiality:

Personal Health Information(PHI) will be safeguarded at all times. Patients will be assigned a study ID number; their name or other identifying information will not be used in any presentations or publications resulting from this research. Data will be kept in a locked office to which only departmental personnel have access. Data files will be stored on a secure hospital network drive.

Sample collection:

Patients will be enrolled prospectively and randomized to either study or placebo arms. In addition, each patient will be assigned a random non-identifiable study number to ensure anonymity.

The following information will be recorded:

Age in months, gender, duration of procedure, duration from induction to extubation, Recovery time (defined as arrival in PACU to first spontaneous eye opening or response to verbal command)

PAED behavioral scoring sheet will be completed at: (T=0 on PACU arrival, 10, 20 and 30 minutes post PACU arrival). Nurse determination of occurrence of ED.

Administration of supplemental dexmedetomidine, propofol, opioid or benzodiazepine in PACU will be noted if given. Opioid given to treat pain will be noted as such.

References:

Sikich N, Lerman J: Development and psychometric evaluation of the Pediatric Anesthesia Emergence Delirium Scale. *Anesthesiology* 2004; 100:1138-45.

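### The plan rules out added risk but specifies no record of injury, dislodgement, respiratory, seizure or light-related events, or of when the lamp goes off

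*Combined protocol and SAP*

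**What the plan says.** All references are to the combined protocol and SAP.

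- **Risk/Discomfort** opens with "The study procedure poses no additional risk to patients. The major risk is loss of confidentiality". It then cites earlier human testing and routine NICU use of the same lamps. It presents the risk of phototherapy as familiar from decades of neonatal treatment and as falling mainly on preterm infants with long, intense exposure. It rules out neonates and exposure beyond 30 minutes. It stops the light once the child is awake and makes purposeful eye contact, and gives avoidance of discomfort as the reason for stopping.
- **Background** says that thrashing during ED "can lead to dislodgement of IV cannulas, surgical dressings and or surgically placed items such as drains and catheters". It also names cardiopulmonary depression as an adverse effect of the added drugs. **Purpose** says that ED "may result in self-inflicted injury (falls and collision with bedframe) or perturbation of intravenous or surgically placed devices".
- **Patient identification** excludes, among others, children with "history of migraine headaches, ocular disorders, seizure history", without giving a reason.
- **Anesthetic Description** says that on PACU arrival "the Drager phototherapy lamp will be illuminated over the patient's head and neck". This applies to both arms, and the light stays on until 30 minutes in PACU.
- **Sample collection** lists age, gender, two durations, recovery time, PAED at 0, 10, 20 and 30 minutes, and the nurse's judgement of ED. On drugs it says: "Administration of supplemental dexmedetomidine, propofol, opioid or benzodiazepine in PACU will be noted if given".
- **Statistical Analysis Plan** contains no safety analysis. The text just before it closes the study after the PACU assessments, with no follow-up.

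**The concern.** The risk statement is categorical, yet the section that contains it allows that phototherapy carries some risk and that the child may be uncomfortable. Elsewhere the plan names physical events that are foreseeable in these children, and it puts equipment above the head of 2 to 6 year olds, some of whom are expected to thrash. None of those events has a place on the data list.

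If the plan is followed as written, a dislodged cannula, contact with the lamp, a respiratory event after rescue sedation or a complaint about the light need not enter the trial data. The trial could then report on ED with nothing to say about these harms by arm, and the analysis could not fill the gap afterwards. Actual exposure would also be unknown, because the time at which the light went off is not listed and two sections give different rules for it.

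**Working it through.** **1. Foreseeable events against recorded items**

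| Event | Where the plan raises it | Listed for recording? |
|---|---|---|
| More ED, higher PAED | Primary aim | Yes |
| More rescue drugs | Secondary aim | Yes |
| IV or device dislodgement | Background, Purpose (as a result of ED) | No |
| Fall or collision | Purpose (as a result of ED) | No |
| Contact with the lamp | Not named; inferred from lamp position | No |
| Respiratory event | Background (adverse effect of added drugs) | Drug only, not the event |
| Discomfort | Risk/Discomfort | No |
| Eye problem, headache, seizure | Only as related exclusions, no reason given | No |
| Lamp-off time | Two different rules | No |

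Recovery time cannot stand in for lamp-off time. It ends at first spontaneous eye opening or response to verbal command, which matches neither rule for ending the light.

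**2. The plan's own sample size**

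Inputs from the Statistical Analysis Plan: p1 = 0.40, p2 = 0.15, two-sided alpha 0.05, power 80%. Allocation is not stated; 1:1 is assumed. The mean rate is 0.275.

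n per arm = [1.960 × √(2 × 0.275 × 0.725) + 0.842 × √(0.40 × 0.60 + 0.15 × 0.85)]² / 0.25² = (1.238 + 0.510)² / 0.0625 = 48.9, so 49 per arm and 98 in total. The stated 98 reproduces. The 110 envelopes in the Randomization section give 55 per arm. The trial is sized for ED only.

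**3. Children expected to have ED at the plan's rates**

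- 98 children: 49 × 0.40 + 49 × 0.15 = 26.95, about 27.
- 110 children: 55 × 0.40 + 55 × 0.15 = 30.25, about 30.

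**4. What zero recorded events would exclude**

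One-sided 95% upper limit = 1 − 0.05^(1/n). Upper end of the exact two-sided 95% interval = 1 − 0.025^(1/n).

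| Harm | n | One-sided limit | Two-sided upper end |
|---|---|---|---|
| Lamp contact, both arms | 98 | 3.0% | 3.7% |
| Lamp contact, both arms | 110 | 2.7% | 3.3% |
| Light-specific, blue-light arm | 49 | 5.9% | 7.3% |
| Light-specific, blue-light arm | 55 | 5.3% | 6.5% |

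**5. What 49 children per arm could show**

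The harm rates here are assumptions; the documents give none.

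- Chance of at least one event among 49 children, 1 − (1 − p)^49: 39% for p = 1%, 63% for 2%, 92% for 5%.
- Power to compare arms, Φ{[d√n − 1.960√(2p̄(1 − p̄))] / √(p1(1 − p1) + p2(1 − p2))}, where d is the difference and p̄ the mean of the two rates. For 2% against 5%: (0.210 − 0.509) / 0.259 = −1.16, about 12%. For 2% against 10%: (0.560 − 0.658) / 0.331 = −0.30, about 38%.

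A checklist would therefore have a fair chance of catching an event that is not very rare, but it could not support a test between arms.

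**The case against.** The case for the plan as it stands is substantial.

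- **Low risk is argued, not merely asserted.** The plan cites prior human studies, workplace use (Background) and NICU use, keeps the plexi shield in place and caps exposure at 30 minutes. A reader might infer that the cited safety record is neonatal only. It is not, although the documents do not show whether the other studies included children of this age. These are good reasons to expect low risk, but they are not data from this trial.
- **The injuries belong to ED.** The plan attributes falls, collisions and dislodgement to ED, which occurs without the study, and rescue treatment is given regardless of participation. Naming them does not contradict a sentence about the study procedure. They matter because they are foreseeable and would differ by arm if the light changed ED.
- **The exclusions prove little.** It is tempting to read them as an admission of light-related danger. No reason is given. The proposed mechanism runs through the retina and EEG, so they may equally protect efficacy.
- **The data list may not be complete.** Weight and ASA category enter the models but are not on it, so one cannot conclude that these events would leave no trace anywhere. What can be said is that no section specifies them.
- **The aims are measured.** A reader might infer that the trial cannot show the benefit that justifies it. The stated aims are ED incidence and rescue use, and both are recorded. Fewer injuries is motivation, not an endpoint.
- **A by-arm table has limits.** Both arms lie under a lamp, so no comparison isolates the risk of the hardware, and power for light-specific harm is low.

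These points narrow the concern. They do not supply the missing items or make the risk sentence fit the rest of its section.

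**Conclusion.** The concern holds in a limited form. The risk statement is stronger than its own section supports, and the plan specifies no recording of harms other than those that show as ED, PAED scores or rescue drug use. A reader might conclude that the trial could not detect harm at all. That goes too far: a worsening of agitation or of rescue use would be recorded, and testing is two-sided.

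The primary analysis is unaffected. What is lost is any event rate from this trial for the unlisted harms, where complete recording with no events would have given the upper limits in step 4. The 5.9% and 5.3% figures apply only to light-specific harm in the blue-light arm. Using them for lamp contact would be wrong, because children in both arms are under the lamp. All per-arm figures assume 1:1 allocation, and the expected ED counts assume the plan's 40% and 15%.

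**What to change.** 1. **Form.** Add tick boxes to the existing PAED sheet for IV or device dislodgement; fall or collision; contact with the lamp, listed separately; respiratory event, with a one-line definition and whether it followed a rescue drug; seizure; eye or light discomfort; and headache. Add lamp-off time and reason. A blinded PACU nurse completes it within the existing 30-minute observation. Two nurses score each child, so state which one fills it in.
2. **Analysis.** Add one table of counts by arm with exact 95% confidence intervals, descriptive and without tests. Report lamp contact over both arms combined. Note that events after 30 minutes are not covered.
3. **Wording.** Replace the opening risk sentence with one saying that risk is expected to be minimal and is monitored.
4. **Reconcile.** Anesthetic Description keeps the light on until 30 minutes in PACU, while Risk/Discomfort ends it at purposeful eye contact. The investigators need to bring the two into agreement.

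The cost is a few extra fields, one table, an amendment and a slightly less favourable risk statement. The numbers will still be too small to compare harms between arms, and the report should say so.

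### The protocol stops the study at first purposeful eye contact but schedules PAED scoring to 30 minutes, and it gives two different light-off rules

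*Combined protocol and SAP*

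**What the plan says.** **When scoring ends.** Postoperative evaluation for emergence delirium sets the PAED schedule for the two nurses: "They will be asked to complete the scoring evaluation upon arrival to the PACU and at 10 minutes, 20 minutes and 30 minutes following arrival". Sample collection repeats it: "PAED behavioral scoring sheet will be completed at: (T=0 on PACU arrival, 10, 20 and 30 minutes post PACU arrival". Neither attaches a condition. The evaluation section then closes with: "The study will end at this point without the need for additional follow-up or patient contact related to the study". Risk/Discomfort gives a different end point: "The study will be terminated the moment the patient is awake and making purposeful eye contact with the PACU RN to avoid unnecessary discomfort".

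**When the light ends.** Anesthetic Description says: "The light will remain active and over the patient until the patient has been in the post anesthesia recovery unit (PACU) for 30 minutes". Risk/Discomfort says: "The moment the patient is awake and making purposeful eye contact with the PACU RN, the lights will be terminated". The same paragraph sets an upper limit on exposure: "This study will not include any neonates (with immature retina) or long term exposure of >30 min".

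**How the analysis treats gaps.** Sample size/Data Analysis says that "missing data for the PAED scores over time indicated a patient woke up or experienced emergence delirium and so no imputation will be performed". It defines emergence delirium (ED) as PAED above 12. It also plans a second logistic model whose outcome is ED or a PAED score of at least 12 at 10, 20 and 30 minutes.

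**The concern.** Two rules collide for any child who is awake and making eye contact before 30 minutes. One concerns the randomised exposure: whether the lamp stays on. The other concerns the outcome: whether PAED scoring continues.

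The second matters more. Background places ED mostly in the first half hour, and the outcome is defined by PAED. If the termination sentence is followed literally, ED that begins after first eye contact but within the window has no PAED score. The stopping trigger is not neutral. Eye contact is one of the five PAED items, and Background credits blue light with raising alertness. Stopping is therefore tied to the outcome scale and possibly to the assigned arm, and the SAP plans no imputation. If blue light wakes children sooner, they would be observed for less time, and ED could look rarer in that arm without being rarer.

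**Working it through.** **1. The texts side by side, for a child who makes eye contact at, say, minute 12**

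| Item | Instruction A | Instruction B |
|---|---|---|
| Light | On to minute 30 (Anesthetic Description) | Off at minute 12 (Risk/Discomfort) |
| PAED at 20 and 30 min | Scored (Postoperative evaluation; Sample collection) | Not scored, if the study has been terminated (Risk/Discomfort) |

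Staff cannot follow both columns. Off when awake, with a 30-minute maximum, would reconcile the light row, but no sentence says so.

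**2. Does the termination sentence reach the scoring?** Its section and its stated purpose, avoiding discomfort, point to the lamp. Two facts point the other way. The lamp already has its own sentence with the same trigger a few lines earlier. And the SAP names waking as a reason for a missing PAED score, which fits scoring that stops at waking. The text does not settle it.

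**3. The plan's sample size.** Inputs from Sample size/Data Analysis: 40% versus 15%, two-sided alpha 0.05, power 80%. I assume 1:1 allocation, which is not stated. With mean proportion 0.275:

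n per arm = [1.960 × √(2 × 0.275 × 0.725) + 0.842 × √(0.40 × 0.60 + 0.15 × 0.85)]² / 0.25² = 48.9, so 49 per arm and 98 in total.

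The stated 98 is reproduced, and this concern does not change it.

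**4. What a loss of late cases would do.** The documents give no time-to-waking data and no rate of ED after eye contact, so every loss share below is an assumption. A lost case is counted as no ED and the child stays in the denominator. Results come from exact binomial enumeration of the two-sided chi-square test at 0.05. The 55-per-arm column assumes that all 110 envelopes in Randomization are used 1:1 and all children are analysed.

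Equal loss f in both arms, with observed rates 0.40(1 − f) and 0.15(1 − f):

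| f | Power, 49/arm | Power, 55/arm |
|---|---|---|
| 0 | 0.809 | 0.852 |
| 5% | 0.781 | 0.826 |
| 10% | 0.751 | 0.799 |
| 12.5% | 0.735 | 0.785 |
| 25% | 0.652 | 0.702 |

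The 5% and 12.5% rows are the 10% and 25% cases with half the loss recovered from nurse or rescue records.

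No true effect (40% in both arms), with the loss shown for sham and blue:

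| Loss, sham / blue | Observed rates | Type I error, 49/arm | Type I error, 55/arm |
|---|---|---|---|
| 0 / 0 | 0.40 / 0.40 | 0.050 | 0.050 |
| 10% / 10% | 0.36 / 0.36 | 0.048 | 0.053 |
| 25% / 25% | 0.30 / 0.30 | 0.049 | 0.051 |
| 10% / 15% | 0.36 / 0.34 | 0.053 | 0.059 |
| 5% / 12.5% | 0.38 / 0.35 | 0.059 | 0.065 |
| 10% / 25% | 0.36 / 0.30 | 0.093 | 0.106 |

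Equal loss costs power and leaves type I error near 0.05. Inflation depends wholly on the assumed imbalance. Excluding children with a lost case, which the SAP's wording also permits, softens it: for 10% / 25% at 49 per arm, type I error is about 0.07 rather than 0.093.

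**The case against.** The strongest reply is that the termination sentence is loose wording for the lamp. It follows directly on the exposure limit, repeats the lamp's trigger and gives comfort as its reason; an observational score causes no discomfort. No sentence orders scoring to stop. The SAP's missing-data sentence also lists ED itself as a cause of missing scores, so it describes something wider than this stopping rule and does not mention it. On this reading the remaining light conflict is a matter of clarification.

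Even on the literal reading, harm needs a chain of events: scoring stops, ED starts after purposeful eye contact, and neither the nurse's determination of ED nor the rescue-drug record captures it. A delirious child who makes no purposeful eye contact never meets the trigger and is still scored. Sample collection records nurse-determined ED and rescue drugs with no eye-contact cut-off, and ED is treated regardless of participation. The second model's outcome is satisfied by recorded ED alone, which suggests ED is also recorded apart from the PAED sheet; later scores are needed only for children not already classified that way.

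Much of this stands. It limits the likely harm and makes the figures above illustrations only. It does not remove the contradiction. The light-only reading leaves the duration of the randomised exposure in conflict. And nothing in the SAP says that a nurse's determination replaces a missing score in an outcome defined by PAED.

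**Conclusion.** The concern holds: the protocol is wrong as written and should be corrected. That the instructions conflict is certain from the text. The effect on the analysis is not. It ranges from none (the light-only reading, or all late ED captured elsewhere) to a material loss of power or an inflated type I error under the assumed losses. At 49 per arm, the assumed equal losses of up to 25% bring power down to as little as 0.65, and the assumed imbalances give type I error from 0.053 to 0.093. These figures rest on assumed loss shares, 1:1 allocation, and lost cases counted as no ED.

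**What to change.** Make three wording changes:

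1. In Risk/Discomfort, limit the termination sentence to the light, so that it switches off the lamp and does not end the study.
2. State one light-off rule in both Anesthetic Description and Risk/Discomfort, applied alike in both arms. For example: off when the child is awake and making purposeful eye contact, 30 minutes at most.
3. Add to the evaluation section: PAED is scored at 0, 10, 20 and 30 minutes, and nurse-determined ED and rescue drugs are recorded to 30 minutes, in every randomised child whether or not the light is on.

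Optionally, record the light-off time. Sample collection has no such field, and its recovery time uses a different trigger (first eye opening or response to command).

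The cost is three sentences. Scoring to 30 minutes is already scheduled, so no visits or staff are added.
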